Protocol – Non-interventional study

1/13

Project/Product Name: AuraOnce performance observation
Study ID: CIS-016

07-OCT-2019

Prospective non-interventional evaluation of insertion and sealing performance of AuraOnce Disposable Laryngeal Mask US Version

NCT04128527

Version: 1.0

Date: 07-OCT-2019

Protocol – Non-interventional study

2/13

Project/Product Name: AuraOnce performance observation
Study ID: CIS-016

07-OCT-2019

INTRODUCTION

The AuraOnce is a class IIa disposable (single use, sterile) flexible supraglottic airway device intended to maintain control of the airway during routine and emergency anaesthetic procedures in fasted patients. The AuraOnce was the first single moulded laryngeal mask with a curvature of the airway tube simulating the anatomy of the throat and was launched in 2004.

This study is initiated to ensure that the device continues to perform as intended.

The CIP was made according to the Council Directive 93/42 EEC of 14 June 1993 and amendment 2007/47/EC (1), the guidelines set out in ISO 14155 (2), ISO 14971 (3), the Helsinki Declaration (4) and the European Commissions General Data Protection Regulation (GDPR) (5).

1. IDENTIFICATION AND DESCRIPTION OF THE INVESTIGATIONAL DEVICE

1.1 Description

The Ambu AuraOnce is intended for use as an alternative to a facemask for achieving and maintaining control of the airway during routine and emergency anaesthetic procedures. The Ambu AuraOnce may also be used where unexpected difficulties arise in connection with airway management. It is only intended for use by medical professionals trained in airway management.

It is a laryngeal mask consisting of a tube with a specially shaped inflatable cuff distally, which conforms to the contours of the hypopharynx and with its lumen facing the laryngeal opening. The distal tip of the cuff presses against the upper esophageal sphincter and the proximal end of the cuff rests against the base of the tongue.

The Ambu AuraOnce contains different versions of "U" and "EU". The only difference between "U" version and "EU" version is that "U" version of AuraOnce does not have an enforced tip on the top of the cuff while "EU" version of AuraOnce has the enforced tip.

The product is single use and delivered sterile.

The product concept comprises eight sizes of laryngeal masks. The correspondence between the product sizes and patient size is as stated in the table:

Mask size	Patient weight	Maximum cuff inflation volume
#1 / #1U	<5 kg	4ml
#1½ / #1½U	5-10 kg	7ml
#2 / #2U	10-20 kg	10ml
#2½ / #2½U	20-30 kg	14ml
#3 / #3U	30-50 kg	20ml

Protocol – Non-interventional study

3/13

Project/Product Name: AuraOnce performance observation
Study ID: CIS-016

07-OCT-2019

#4 / #4U	50-70 kg	30ml
#5 / #5U	70-100 kg	40ml
#6 / #6U	>100 kg	50 ml

1.3 Models/type of the investigational device

The product concept comprises eight sizes of laryngeal masks. The Ambu AuraOnce is a sterile and single use device. The product specifications are described in the table below.

	Mask size							
	#1	#1½	#2	#2½	#3	#4	#5	#6
① Airway connector	15 mm male (ISO 5356-1)							
② Min. I.D. Tube	5,2 mm	7,3 mm	8,6 mm	8,5 mm	8,5 mm	9,6 mm	10,6 mm	11,3 mm
③ Max. O.D. Tube	10,5 mm	13 mm	15 mm	17,5 mm	17,5 mm	20 mm	22,5 mm	25 mm
④ Inflation Valve	Luer cone compatible with ISO 594-1							
Appropriate storage temperature	10 °C (50 °F) to 25 °C (77 °F)							
Dimensions (mm) (length x width x height)	97x 24x70	112x 29x82	128x 34,5x95	148x 41x109	148x 49x116	168x 56x132	187x 64x148	200x 69x165
Weight	9,8 g	13,5 g	19,4 g	28,1 g	30,8 g	44,2 g	62,3 g	76,6 g
Internal volume of ventilatory pathway	5,5 ml	8 ml	11 ml	15 ml	16 ml	21 ml	30 ml	38 ml
Pressure drop	<1,2 cmH ₂ O at 15 l/min	<0,8 cmH ₂ O at 15 l/min	<1,0 cmH ₂ O at 30 l/min	<0,8 cmH ₂ O at 30 l/min	<2,0 cmH ₂ O at 60 l/min	<1,2 cmH ₂ O at 60 l/min	<0,8 cmH ₂ O at 60 l/min	<0,5 cmH ₂ O at 60 l/min
Min. interdental gap	15 mm	17 mm	19 mm	21 mm	25 mm	29 mm	31 mm	32 mm
⑤ Internal pathway	10,3 cm	12,0 cm	13,8 cm	15,9 cm	15,9 cm	17,8 cm	20,0 cm	22,0 cm

1.4 Device traceability

The site included in the study will make their daily used bronchoscopes available for the procedure.

Protocol – Non-interventional study

4/13

Project/Product Name: AuraOnce performance observation
Study ID: CIS-016

07-OCT-2019

The site will free of charge receive 20 Ambu® AuraOnce devices in each adult size (size 3, 4 and 5). Any devices remaining after the end of the study will be accounted for and shall be returned to Ambu®.

There are no requirements regarding device accountability for CE marked devices. However, for logistical reasons the Sponsor will account for all devices delivered to and returned from the Investigators in a Device Accountability Form kept at Sponsor's address.

1.5 Investigational device procedures

The laryngeal mask is introduced in the routine fashion by trained staff (anesthesiologist or anesthesia nurse). It will be used in already planned diagnostic flexible bronchoscopy procedures in general anesthesia. The flexible bronchoscope is introduced through the laryngeal mask and special attention is paid to the cuff area including the tip.

2. JUSTIFICATION FOR THE DESIGN OF THE CLINICAL INVESTIGATION

The clinical investigation is an observational study designed as quality control of the AuraOnce. Based on experience, the sample size has been judged to be adequate to provide the information necessary to show a representative picture of the product quality which is the objective of the study.

3. OBJECTIVES AND HYPOTHESES

The objective of this study is to observe the performance of the AuraOnce through clinical assessment and endoscopic imaging to ensure ongoing documentation on quality of the product in regards to correct placement remains high.

This is an observational study with no hypothesis. However, a success criterion is set saying that in 90% of the cases the AuraOnce must be correctly centred above vocal cords with no clinical significant air leak and using maximum three placement attempts.

3.1 Primary

Primary endpoint¹:

- Leakage (yes/no), if yes insert signs of leakage

3.2 Secondary

Secondary endpoints²:

- Questionnaire – interview to anaesthesiologist/nurse
 - o Ease of insertion (5-point scale, very difficult to very easy)
 - o Ease of obtaining seal (5-point scale, very difficult to very easy)
 - o Overall performance (5-point scale, very bad to excellent)
- Opening placed just above vocal cords (yes/no) correct positioning is documented by endoscopic picture (including POGO score)

¹ Primary endpoint(s) is (are) principal indicator(s) used for assessing the primary hypothesis of a clinical investigation. It is also used to calculate sample size.

² Secondary endpoints are indicators used for assessing the secondary hypotheses of a clinical investigation.

Protocol – Non-interventional study

5/13

Project/Product Name: AuraOnce performance observation
Study ID: CIS-016

07-OCT-2019

- Folding of tip (yes/no) - is documented by endoscopic picture

3.3 Claims and intended performance

The claims to be observed in the study is:

- Ease of insertion
- Tip resists folding over during insertion and plugs the upper oesophageal sphincter
- Sealing

4. DESIGN OF THE CLINICAL INVESTIGATION

4.1 General

This study is designed as a single-center, prospective observational, non-controlled, non-interventional study with an investigation period lasting for one day (during one bronchoscopy procedure). The study will take place in Denmark.

The study will include minimum 15 adult patients planned for a diagnostic flexible bronchoscopy procedure in general anaesthesia using a laryngeal mask.

The involved site will include subjects during a one month period, October 2019. However, the study will not be initiated before the study protocol is duly approved, i.e. by site, Ambu and Ethics Committee if relevant (if EC approval is not needed a written opinion from the EC must be obtained). If the number of subjects cannot be included in time, the sponsor will decide whether the study period should be extended, or the study should be closed.

The intention is to perform a quality assessment of the AuraOnce. Subjects will not be asked to participate in this study as it is a quality study (see section 16) where the AuraOnce is used within its intended use and according to normal clinical procedure.

4.2 Investigational devices and comparators

4.2.1 Device exposure

The subjects will be exposed to the device for less than an hour. The devices used for the study are all CE marked and used in normal clinical practice.

4.2.2 Choice of comparator

Not applicable

4.2.3 Other investigational devices or medications

Apart from the AuraOnce Laryngeal mask, the following devices can be used during the procedure:

- Flexible bronchoscope normally used for the planned bronchoscopy procedure at site.
- Syringes with saline for broncho-alveolar lavage (BAL)
- Biopsy forceps for transbronchial biopsy (TBB).

Protocol – Non-interventional study

6/13

Project/Product Name: AuraOnce performance observation
Study ID: CIS-016

07-OCT-2019

4.2.4 Number of investigational devices to be used

One AuraOnce is expected to be used for each procedure. In case of device deficiencies, the product must be replaced, and a device deficiency form must be completed.

4.3 Subjects

The clinical investigation will be conducted on minimum 15 subjects and maximum 20 subjects enrolled in one clinical investigation site.

4.3.1 Inclusion criteria

Subjects will be enrolled responding to the following criteria:

- Subjects > 18 years
- Subjects planned for diagnostic flexible bronchoscopy procedure in general anesthesia using a laryngeal mask.

4.3.2 Exclusion criteria

Subjects responding to the following criteria are excluded from participation:

- Subjects where use of AuraOnce cannot be clinically justified

4.3.3 Subject withdrawal or discontinuation

Patients not completing the clinical procedure as intended by the investigator are considered as drop-outs as the evaluation form will lack information of the device. In case of drop-outs the study will not be completed until the minimum number of subjects is included.

Subjects will be withdrawn from the clinical investigation for the following reason:

- a. Withdrawal by investigator for e.g. safety reasons

The reason for withdrawal will be investigated and carefully documented in the appropriate section of the case report form (CRF).

If a subject is replaced the new subject is given a new subject number.

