4.3.5 Duration of the clinical investigation

The data collection is expected to last three days within a two months period. The subjects are included in the study when the investigator has ensured that they fulfill the in- and exclusion criteria and they are completed when the bronchoscopist have confirmed the laryngeal mask placement (by taking a picture) and starts the planned bronchoscopy procedure. The expected duration of each subject's participation is estimated to be less than one hour.

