4.4 Procedures

The site will receive the protocol, AuraOnce and case report forms (CRFs). A total of 80 Aura once products will be provided, included 20 laryngeal masks in each size (size 3, 4, 5). Any remaining products after the study will be returned to Ambu A/S.

During normal clinical bronchoscopy procedures where general anaesthesia with a laryngeal mask is needed AuraOnce will be used if the subjects fulfil the in- and exclusion criteria. The CRF must be filled in for each subject that is enrolled in the investigation.

The investigation period for each subject is within one day. The anaesthesiologist decides which size of AuraOnce should be used for each subject and places the laryngeal mask according to normal clinical practice at the site.

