4.4.7 Bronchoscopy procedure

Prior to the bronchoscopy procedure, which the patient is scheduled for, an assessment of the AuraOnce will be performed.

- The head of the patient is placed in neutral position.
- A lubricated flexible video bronchoscope is inserted through the AuraOnce.
- A picture is taken of the vocal cords to assess the placement of AuraOnce
 - The picture is kept with the CRF
- The percentage of glottic opening (POGO), defined on a scale from 0-100 (see figure below) is used to confirm correct placement (6). The percentage of opening seen indicates whether AuraOnce is able to adapt to the anatomy.

- A picture of the AuraOnce cuff is taken, specially focussing on the tip
 - The picture is printed and kept with the CRF
 - If any issues with the cuff is observed (especially folding) it must be described in the CRF.

After assessing the AuraOnce the diagnostic flexible bronchoscopy procedure is performed as planned and the AuraOnce is removed after the procedure. The bronchoscopic procedure and removal of AuraOnce is not part of this investigation, and the study ends as the bronchoscope passes the vocal cords.

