6.3.2 Handling of dropouts and missing data

Patients not completing the clinical procedure as intended by the investigator are considered as drop-outs as the evaluation form will lack information of the device. Drop-outs are

Protocol – Non-interventional study

11/13

Project/Product Name: AuraOnce performance observation
Study ID: CIS-016

07-OCT-2019

compensated in the sample size estimation to ensure that a complete data set is collected for minimum 15 patients. Missing data will not be imputed.

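### The drop-out rule in 4.3.3 and 6.3.2 rests on an undefined clinical procedure, so a patient with a complete device assessment can be classed as a drop-out and replaced after the outcome is known

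*Combined protocol and SAP*

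**What the plan says.** **The rule.** Section 4.3.3 reads: "Patients not completing the clinical procedure as intended by the investigator are considered as drop-outs as the evaluation form will lack information of the device". Section 6.3.2 repeats it, with the same reason: such patients are "considered as drop-outs as the evaluation form will lack information of the device".

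**What follows from being a drop-out.** Section 4.3.3 adds: "In case of drop-outs the study will not be completed until the minimum number of subjects is included". It also provides that a replacement subject gets a new number. Section 6.3.2 says that drop-outs are allowed for in the sample size so that at least 15 patients have complete data, and that nothing is imputed.

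**When a subject is complete.** Section 4.3.5 says of subjects: "they are completed when the bronchoscopist have confirmed the laryngeal mask placement (by taking a picture) and starts the planned bronchoscopy procedure". Section 4.4.7 says: "The bronchoscopic procedure and removal of AuraOnce is not part of this investigation, and the study ends as the bronchoscope passes the vocal cords".

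**When outcomes are recorded.** By 4.4.6, the number of attempts, leakage and the three user ratings are noted at or after insertion. By 4.4.7, the vocal-cord picture with its POGO score and the cuff and tip picture are taken before the scheduled bronchoscopy.

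**The criterion.** Section 6.2 requires 90% of cases to meet three conditions: correct centring, no clinically significant leak, and at most three attempts. It does not say which patients count as cases.

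**The concern.** The rule removes a patient because the form will be incomplete, but its trigger is an event that, on the natural reading, comes after the form has been filled in. If a bronchoscopy is changed or cut short once the pictures have been taken, the patient is complete under 4.3.5 and a drop-out under 4.3.3.

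The timing matters. Whether a patient counts would be settled after the device result is known, in an open, uncontrolled study, by reference to what the investigator intended. If the reason for the change is connected with the mask, failures could be lost selectively. If it is not, valid observations are still lost from a sample of at most 20.

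Read narrowly, as covering incomplete forms only, the rule has a different weakness. A mask that could not be seated, so that no picture was taken, also leaves an incomplete form, and that device failure could be replaced as a drop-out.

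**Working it through.** The plan has no figure to reproduce: 6.1 says no sample size calculation was done, and no drop-out rate appears anywhere. The check therefore compares the sections and then counts.

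**Step 1. Each part of the 6.2 criterion against the point where it is recorded.**

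| Item | Recorded under | Before the bronchoscopy? |
|---|---|---|
| Number of attempts | 4.4.6 | Yes |
| Leakage | 4.4.6 | Yes |
| Position above the cords | 4.4.7 | Yes |

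The secondary items (three ratings, tip folding) are also recorded by then. Nothing is collected once the bronchoscope passes the cords. For a patient whose bronchoscopy is altered after that point, the reason given in 4.3.3 is not true: the form lacks nothing.

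**Step 2. Successes needed to pass.** The smallest r with r/n ≥ 0.90, for n = 15 to 20 (4.3 and 6.1):

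| n | 0.9 × n | r needed | Failures allowed |
|---|---|---|---|
| 15 | 13.5 | 14 | 1 |
| 16 | 14.4 | 15 | 1 |
| 17 | 15.3 | 16 | 1 |
| 18 | 16.2 | 17 | 1 |
| 19 | 17.1 | 18 | 1 |
| 20 | 18.0 | 18 | 2 |

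**Step 3. Effect of leaving out one assessed patient.**

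- One failure left out, with two failures among 16 to 19 assessed: 14/16 = 87.5% becomes 14/15 = 93.3%; 15/17 = 88.2% becomes 15/16 = 93.8%; 16/18 = 88.9% becomes 16/17 = 94.1%; 17/19 = 89.5% becomes 17/18 = 94.4%. Each moves from fail to pass.
- One success left out, with two failures among 20 assessed: 18/20 = 90.0% becomes 17/19 = 89.5%, from pass to fail.
- With three failures among 20 (17/20 = 85.0%), leaving out one failure gives 17/19 = 89.5%, still a fail. Two would have to go: 17/18 = 94.4%.

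A flip therefore needs a borderline count.

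**Step 4. Size of a selective loss, under assumed rates.** Let p be the true success rate and q the share of failures classed as drop-outs and replaced, with 15 analysed and the ceiling of 20 ignored. The success rate among those analysed is p' = p / [p + (1 − p)(1 − q)]. The chance of passing is P(X ≥ 14) = 15 p'^14 (1 − p') + p'^15.

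For p = 0.85 and q = 0.25, p' = 0.85 / (0.85 + 0.15 × 0.75) = 0.85 / 0.9625 = 0.883.

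| Assumed p | q = 0 | q = 0.25 | q = 0.50 |
|---|---|---|---|
| 0.80 | 0.167 | 0.290 | 0.491 |
| 0.85 | 0.319 | 0.463 | 0.654 |
| 0.90 | 0.549 | 0.677 | 0.815 |
| 0.95 | 0.829 | 0.891 | 0.945 |

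Both p and q are assumptions. If drop-out is unrelated to the device outcome, there is no systematic bias, and only the single-patient effect of step 3 remains.

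**The case against.** The best defence is that the rule can be read consistently with the rest of the plan. The term is undefined and does not always mean the bronchoscopy: 4.4.5 uses similar words for preparing and sizing the mask, and 4.1 for ordinary use of the AuraOnce. The reason attached to the rule points to patients whose form is incomplete, 6.3.2 aims at complete data, and a subject already complete under 4.3.5 arguably cannot drop out later. Section 6.3.1 also promises descriptive statistics for all measured outcomes. The study has no hypothesis, and any 90% threshold at this size turns on single patients.

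Much of this stands. The sections contradict each other on one reading, not on every reading. A reader might infer that the plan orders assessed patients to be discarded. It does not: no sentence says that a drop-out's data are deleted or leave the 6.2 denominator, and recruitment after drop-outs is required only until 15 is reached. A reader might also infer that failures will be removed selectively, for example through a poor seal that shortens the bronchoscopy. That is possible, but nothing in the documents shows that it will happen or how often.

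The defence does not dispose of the point. Bronchoscopy remains the natural reading: patients are enrolled because one is planned, 4.4 places use of the mask "During normal clinical bronchoscopy procedures", and 4.4.7 separates the mask assessment from the procedure for which the patient is scheduled. Continuing recruitment and allowing for drop-outs in the sample size make sense only if drop-outs do not count. If two readings are open, the choice between them could be made after the result is seen. The narrow reading leaves failed placements exposed.

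**Conclusion.** The concern holds as a conditional one. If the clinical procedure means the bronchoscopy, 4.3.3 and 6.3.2 conflict with 4.3.5, 4.4.6 and 4.4.7, and a patient with a full device assessment can be classed as a drop-out and replaced after the outcome is known. That such a patient leaves the 6.2 denominator is a strong inference, not a stated rule.

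The size is one patient at a borderline count: two failures among 16 to 19 with one of them left out, or exactly two among 20 with a success left out. Away from those counts, one reclassification does not change the verdict. The passing probabilities in the working rest on assumed success and loss rates and show direction only.

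The correction should be made, because 6.2 is the plan's only pass/fail rule and its denominator is open to a choice made after the result.

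**What to change.** In 4.3.3 and 6.3.2, replace the definition and its reason with wording to this effect:

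- A drop-out is a subject in whom the assessments in 4.4.6 and 4.4.7 were not obtained, for reasons unrelated to mask placement or seal.
- A subject with those assessments recorded is complete under 4.3.5, stays in all analyses and in the 6.2 denominator whatever happens in the bronchoscopy, and is not replaced.
- An attempted placement that fails, so that no picture is taken, counts as a failure in 6.2.

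In 6.2, state the denominator to match: all enrolled subjects except drop-outs as defined above.

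The cost is a few sentences in three sections. The planned 15 to 20 patients need not change, and fewer replacements may be needed. The pass rate may move slightly in either direction, most likely to a slightly less favourable figure, because failures that could have been set aside will now count.

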4.3.4 Recruitment and point of enrolment

The subjects (patients) included in this study are scheduled for a diagnostic flexible bronchoscopy procedure in general anesthesia using a laryngeal mask.

When a subject is included, the investigator assures that the subject meets all inclusion criteria and none of the exclusion criteria, by checking the relevant boxes in the CRF.

The subjects will not receive information about the study, as no patient data are obtained, and the CE-marked AuraOnce laryngeal mask is used within intended use. The only data to be obtained are evaluation forms directly related to the performance of the device, the user's perception of insertion of the laryngeal mask and pictures of the placement and sealing.

4.3.5 Duration of the clinical investigation

The data collection is expected to last three days within a two months period. The subjects are included in the study when the investigator has ensured that they fulfill the in- and exclusion criteria and they are completed when the bronchoscopist have confirmed the laryngeal mask placement (by taking a picture) and starts the planned bronchoscopy procedure. The expected duration of each subject's participation is estimated to be less than one hour.

4.4 Procedures

The site will receive the protocol, AuraOnce and case report forms (CRFs). A total of 80 Aura once products will be provided, included 20 laryngeal masks in each size (size 3, 4, 5). Any remaining products after the study will be returned to Ambu A/S.

During normal clinical bronchoscopy procedures where general anaesthesia with a laryngeal mask is needed AuraOnce will be used if the subjects fulfil the in- and exclusion criteria. The CRF must be filled in for each subject that is enrolled in the investigation.

The investigation period for each subject is within one day. The anaesthesiologist decides which size of AuraOnce should be used for each subject and places the laryngeal mask according to normal clinical practice at the site.

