8. DEVICE ACCOUNTABILITY

The site included in the study will make their daily used bronchoscopes available for the procedure.

The site will free of charge receive 20 Ambu® AuraOnce devices in each of the sizes used for adults (size 3, 4, 5 and 6). Any devices remaining after the end of the study will be accounted for and shall be returned to Ambu®.

There are no requirements regarding device accountability for CE marked devices. However, for logistical reasons the Sponsor will account for all devices delivered to and returned from the Investigators in a Device Accountability Form kept at Sponsor's address.

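### Does the mismatch between 80 masks and three sizes at 20 each (60), with differing size lists in sections 1.4, 4.4 and 8, require a change to the plan?

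*Combined protocol and SAP*

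**What the plan says.** Three places in the combined protocol and SAP describe the free supply of masks to the single site.

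- Section 1.4 (Device traceability) promises 20 "AuraOnce devices in each adult size (size 3, 4 and 5"). It gives no total.
- Section 4.4 (Procedures) gives a total and a list: "A total of 80 Aura once products will be provided, included 20 laryngeal masks in each size (size 3, 4, 5").
- Section 8 (Device accountability) promises 20 "AuraOnce devices in each of the sizes used for adults (size 3, 4, 5 and 6"). It gives no total.

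Section 1.1 sets out the eight mask sizes by patient weight: "The correspondence between the product sizes and patient size is as stated in the table". In that table size 5 covers 70 to 100 kg and size 6 covers patients above 100 kg. Eligibility sets no weight limit. The inclusion criteria ask for "Subjects > 18 years" and a planned bronchoscopy under general anaesthesia with a laryngeal mask. The one exclusion is "Subjects where use of AuraOnce cannot be clinically justified". On the choice of mask, section 4.4 says "The anaesthesiologist decides which size of AuraOnce should be used for each subject".

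**The concern.** Section 4.4 contradicts itself on a plain reading, because its list does not add up to its total. Sections 1.4 and 8 then give different lists of adult sizes for the same delivery, and both cannot be right.

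The difference is one whole size, and the size in question is the one that the table in section 1.1 assigns to patients over 100 kg, who are eligible. If that size were not at the site, such patients might be judged unsuitable for the device at screening and never enrolled. The plan asks for a case report form for enrolled subjects only ("The CRF must be filled in for each subject that is enrolled in the investigation") and describes no record of patients screened out. The report could then rest on a narrower range of sizes and patients than a reader would assume, in a study that section 2 says should give a representative picture of product quality.

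**Working it through.** **Inputs.** Masks per size: 20 (sections 1.4, 4.4 and 8). Sizes listed: three in sections 1.4 and 4.4, four in section 8. Stated total: 80 (section 4.4). Subjects: 15 to 20 (sections 4.3 and 6.1). Masks expected per procedure: one, with replacement after a device deficiency (section 4.2.4).

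**Step 1: reproduce the stated total.** Total = number of sizes × masks per size.

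| Size list | Calculation | Matches 80? |
|---|---|---|
| Sizes 3, 4, 5 (sections 1.4, 4.4) | 3 × 20 = 60 | No |
| Sizes 3, 4, 5, 6 (section 8) | 4 × 20 = 80 | Yes |

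The gap is 80 − 60 = 20 masks, and 20 / 20 = 1 size. Section 4.4's total therefore agrees with section 8's list but not with its own. One size left out of the lists in 1.4 and 4.4 is a plausible origin, but the documents do not prove it.

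**Step 2: try the charitable reading of 4.4.** If the word before the list means that the three sizes are only part of the total, the sum is incomplete rather than wrong: 60 masks in named sizes plus 20 in a size not named. This does not reconcile section 1.4 with section 8, since each presents its list as the adult sizes. That conflict survives every reading.

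**Step 3: compare supply with expected use.** At one mask per procedure, expected use is 15 to 20 masks, plus any replacements. Both 60 and 80 exceed 20 in total. This comparison is across sizes only: it does not show that every size is on hand. If all 20 subjects needed the same size, its 20 masks would be used up with none spare for replacements.

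**Step 4: trace the count into the statistics.**

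- Primary endpoint (section 3.1): leakage, yes or no, in each subject. The number of masks supplied does not enter.
- Success criterion (section 6.2): in 90% of cases, correct position, no clinically significant leak and at most three attempts. Numerator and denominator count cases, not masks delivered.
- Sample size (section 6.1): 15 to 20, with no calculation performed. The supply count is not an input.
- Analysis (section 6.3.1): descriptive summaries of measured outcomes. Nothing is planned by size supplied.

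Replacing 80 by 60, or one size list by the other, changes no formula, threshold or rule in the plan.

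**Step 5: test the route through screening.** For the slip to affect enrolment, three things must hold: the size is not delivered, the site has no other stock of it, and lack of stock leads to exclusion. The first is what the sections disagree about. On the second, no section says that the sponsor is the only source, and section 4.2.1 describes the devices as used in normal clinical practice. On the third, section 4.4.1 tests clinical justification and the inclusion criteria; it does not mention stock. The documents also give no share of patients over 100 kg, so no number of affected subjects can be derived.

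**The case for a change.** The best case for a change is that these are operative statements in a version 1.0 protocol, not superseded text or a broken table, and that they leave open whether the table's size for some eligible adults is delivered. Mask size is not among the items that sections 4.4.4 to 4.4.7 say are recorded. The Device Accountability Form is described as tracking delivery and return, not the size used in each subject. On this view the sponsor should settle the list, record size per subject, keep an anonymous count of patients screened out for want of a size, and state in the report which sizes were used. The cost would be small.

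The inconsistency itself stands in full, and so does the observation that eligibility has no weight limit. The rest does not carry. The case report form is not in the documents, so the absence of a size field from the items named in the text does not show that the form lacks one. A count of patients who were never enrolled would go beyond the data that section 4.3.4 limits the study to: evaluation forms, user perception and pictures. It would also guard against an event for which the documents give no evidence. A report that describes which devices were used is ordinary practice and needs no rule in the plan.

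**Conclusion.** The slip is confirmed: 60 masks from the list against 80 stated in section 4.4, a gap of 20 masks or one size, and three sizes in section 1.4 against four in section 8. It is clerical and concerns logistics. The sponsor can bring the three sentences into line when the device list is settled for delivery, and its accountability form will show what was sent and returned. This review does not say which list is right.

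No change to the design, endpoints, sample size, success criterion or analysis follows, because none of them uses the supply count. The conclusion rests on two points from the documents: at most 20 subjects with one mask expected for each, and a screening rule framed in terms of clinical justification rather than stock. It would need another look only if the sponsor's delivery were shown to be the sole source of masks and patients were turned away for lack of a size. The documents show neither.
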